This study will add affect-based physical activity goals to an existing mHealth intervention called MyDayPlan, which delivers morning and evening goal sessions. Every Sunday, participants receive a text message with a link to a brief REDCap questionnaire where they are asked about their tentative sleep and physical activity schedule for that upcoming week. On days participants have planned to do physical activity (according to the Sunday scheduling survey), they will engage in two goal sessions: one in the morning and one in the evening. Participants are alerted to complete a session with a text message that has a link to a REDCap form. Morning goal sessions provide an activity goal for the day (“goal module”); ask the participant to create a concrete plan for achieving this goal (“action plan module”); and prompt the participant to anticipate barriers and brainstorm solutions to accomplish the goal (“coping plan module”). Evening goal sessions have participants reflect on whether they were able to meet this goal (“self-monitoring module”). The focus of the goal module differs according to the participant’s assigned condition. For each condition, the Fitbit Versa smartwatch will feature a custom watch face with a clock (current local time), the date, current device battery levels, and a physical activity button. The physical activity button can be pressed whenever a subject wants to engage in physical activity, and provides real-time feedback on activity duration. If the subject’s moving average HR is too low following the physical activity button press, the Fitbit smartwatch will ask “Still exercising?” twice (options No; Yes) before auto-concluding the session. [Note: for the Comparison Study, the wording of this question will be “Still being physically active?”]. Participants will also have the option to view short explanatory videos throughout their participation that summarize aspects of what is expected of them in the study.

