slightly varied wording to promote a sense of novelty. Examples of the three prompts are: “(1) Think about the most positive part of your physical activity session today. What about this part made it positive to you? (2) Next, think about the positive feelings you experienced during this session. Please describe them. (3) Take a moment to appreciate your physical activity session today. What about it are you grateful for?”. Savoring prompts will rotate daily and have a day lag built in every week (i.e., Week 1 Monday Savoring Prompts are Week 2 Tuesday Savoring Prompts).

[figure not shown]
Instrumentation

Study variables will be collected with online questionnaires via REDCap surveys, smartwatch-based EMA (“check-ins”), smartwatch-based accelerometry, and an exit interview (Formative Study only).

Fitbit Versa smartwatch accelerometer: Participants will be loaned a Fitbit Versa smartwatch to be worn on the wrist for the duration of the study period, except while bathing. An internal accelerometer continuously measures physical activity intensity (sedentary, light, moderate, vigorous) and step count at the minute-level. **Heart rate (covariate)** is also recorded continuously and is used to determine smartwatch wear, as well as to calculate average heart rate during activity sessions >10 min. Only days with sufficient wear time (defined as ≥ 10 hours of valid data, where no more than 20 minutes per hour has a consecutive step count of zero) are used for analysis. **Daily steps and minutes of light, moderate, and vigorous physical activity (outcome)** are then calculated from minute-level data. Fitbit does not provide access to the raw acceleration data. However, activity intensities, steps, and heart rate measured by Fitbit devices have been shown to be reliable and valid as compared to other activity monitors including Actigraph.⁴²⁻⁴⁵

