EMA via Fitabase Engage: Real-time prompted EMA (“check-ins”) will be administered on the smartwatch using Fitabase Engage. If no interaction with the watch face is made, one reminder signal may be emitted before the prompt becomes inaccessible. EMA (“check-ins”) take approximately 30 seconds to complete. If a prompt occurs during an incompatible activity (e.g., driving), participants will be instructed to ignore it. To minimize participant burden, all questions are answered by tapping the smartwatch interface.^{46,47} **Three types of EMA (“check-ins”)**—random, event-contingent, and evening—will be sent to participants. Random and event-contingent are used for the Formative Study, while the Comparison Study will use event-contingent and evening. **Random EMA** (“check-ins”) will be randomly scheduled to be sent during normal waking hours, with a single prompt sent during each of four evenly spaced time windows: 0-4, 4-8, 8-12-, and 12-16-hours post-waking. Participants are asked to report their incidental affect via seven bipolar Likert Scale items. Five items (Energetic-Fatigued, Happy-Discouraged, Relaxed-Tense, Excited-Bored, Satisfied-Frustrated) are drawn from Russell’s Circumplex Model of Affect;⁴⁸ one (Good-Bad) represents core affective valence;⁴⁹ and one (Proud-Embarrassed) represents self-conscious emotion.⁵⁰ One of these seven items is repeated as a validity check (i.e., for a total of eight items). **Event-contingent EMA** (“check-ins”) are triggered when Fitbit sensors detect physical activity via moving average heart rate max. At least a 10-minute buffer (Formative Study) or 30-minute buffer (Comparison Study) separates the first and second event-contingent EMA during a single exercise bout, such that the moving average heart rate is “reset” following completion of the first prompt and the earliest possible second prompt is sent at least 10-minutes later (Formative Study) or 30-minutes later (Comparison Study) assuming the aforementioned threshold is met. A maximum of two event-contingent EMA will be sent within any given 60 min period. Participants are asked to safely pause their activity to answer questions about their **affective response (mediator)**^{49,51,52} with the same eight (i.e., 7 unique + 1 repeated) items as the random EMA above. Event-contingent EMA also include end a Rating of Perceived Exertion (RPE) item and end by asking whether the current physical activity is the participant’s planned session.⁵³ Finally, evening EMA (“check-ins”) are sent to participants at 8 pm local time every day and ask participants to report their feelings from that day using the same eight affective response items as the random and event-contingent EMA (only modified to ask about their overall affect from that day, rather than their current affect). A depiction of the daily intervention strategies and measures is shown in Figure 2.

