
Figure 2. Daily eMOTION Intervention and Prompting Schedule

Note. ^a Used in the Formative Study; ^b Used in the Comparison Study.

REDCap surveys during morning and evening goal sessions are scheduled to be sent at the same time every day: 5:00 AM with approximately 5 reminders sent once every hour (morning goal session), and 6:00 PM with approximately 5 reminders sent once every hour (evening goal session). Sessions are sent via text message and completed via REDCap. These sessions will deliver the intervention components, as discussed above. Morning goal sessions also assess **affectively-charged motivations (mediator)**⁵⁴ with one item from the Attraction-Antipathy subscale of the AFFEXX,⁵⁵ and **anticipated affect (mediator)** with another item.⁵⁶ The morning goal session also measures incidental affective states using the same 7 items as the random and event-contingent EMA, stress,⁵⁷ pain,⁵⁸ fatigue,⁵⁹ illness, and sleepiness⁶⁰ as key **situational factors (moderator)**. Finally, the participant is asked whether they want to set a physical activity plan for that day, and whether their plan from the day before is the same or different from the plan they want to set for that day. Evening goal sessions measure **physical activity type** and **context (covariates)** by asking participants to report characteristics about the physical activity they performed that day (e.g., running, dance, hiking, home, park, alone, with spouse, perceived exertion⁵⁸). They are also asked if they enjoyed the activity they did (if receiving affect-based goals) and whether they focused on their goal during physical activity. Three questions ask about the extent to which that day's physical activity satisfied various psychological needs.

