Exploratory analysis will examine the distributions, identify needed data transformations, investigate multicollinearity, and identify extreme observations. Data will be analyzed with SAS and R. Missing data analyses will involve considerations of imputation methods,^{93,94} attrition propensity scores⁹⁵ based on the compliance/dropout for each participant,⁹⁶ and sensitivity analyses. We will consider age, sex, income, Version 04.02.25

race/ethnicity, BMI, and fitness as confounders. Other variables associated with outcomes ($p < .10$) will be included as covariates. Exploratory tests of moderation will also be conducted, as there may be sex and age differences in physical activity^{97,98} and affective mechanisms.^{99–101} Power estimates were evaluated using Monte Carlo simulations in Mplus.^{102–105} The estimated effect size of affect-based physical activity interventions range from a small effect on the primary outcome (affective response) ($f^2 = 0.04$, representing a 0.3 point increase on a 5-point affect scale)⁵⁴ to a medium effect on the secondary outcome (physical activity) ($f^2 = 0.17$, representing a 30/min week increase in MVPA).¹⁰⁶ A sample of $N=200$ participants (100 per condition) (after ~30% attrition) is needed to detect small between-subject effects on change in the outcomes (H2 and H3) with $\beta = .80$ and $\alpha = .05$. To detect within-subject effects (H1 and H4), our level-1 sample sizes will be much larger (e.g., $200 \times 4 \times 4 \times 7$ level-1 N for daily data). Thus, we should have sufficient power to detect very small effects for the remaining associations. H5 is exploratory and not statistically powered.

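### The p<.10 covariate rule has no timing limit, so as written it can admit heart rate, activity type and context measured during the intervention into the H1 and H2 treatment-effect models

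*Combined protocol and SAP*

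**What the plan says.** The Comparison Study part of Data Analysis names age, sex, income, race/ethnicity, BMI and fitness as confounders to consider. It then sets a rule: "Other variables associated with outcomes ($p < .10$) will be included as covariates". The rule is mandatory in tone, and no covariate list is given for any single model. Under Aim 1, H1 to H3 are tested by intent to treat, in a separate random-effects model for each treatment effect and outcome.

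Under Instrumentation, the same label is attached to measures taken while participants are on treatment:

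- Heart rate: "Heart rate (covariate) is also recorded continuously". It is also used to "calculate average heart rate during activity sessions >10 min".
- Activity type, and "context (covariates) by asking participants to report characteristics about the physical activity they performed that day", both collected in the evening goal session.

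The Baseline Questionnaire paragraph labels demographics and traits as covariates too, so the label does not separate baseline from on-treatment variables.

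The Intervention section shows that the conditions act on these measures. The intensity condition sets minimum heart-rate goals (Table 3). Affect-based goals are goals about a type or a context. The TYPE/CONTEXT enhancement recommends types and contexts.

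**The concern.** Adjusting for a variable that assignment changes does not, in general, estimate the effect of assignment. Two things can go wrong. If part of the effect runs through the variable, adjustment removes that part. If something unmeasured, such as how the person feels that day, drives both the variable and the outcome, adjustment creates a spurious difference, possibly in the other direction.

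The exposure differs by hypothesis. For H1, heart rate, type and context are all affected. For H2 it is mainly type and context, which are the route TYPE/CONTEXT is meant to use. The point is weaker for H3. For affectively-charged motivations, measured in the morning, later same-day heart rate or activity cannot be a mediator.

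The trial uses a MOST design to determine the effect of each component. A component that works through activity choice could look weaker than it is, and an H1 difference in activity could be shrunk or manufactured. Because the direction is not known in advance, the error cannot be treated as conservative.

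**Working it through.** **1. The plan's own figure.** The plan gives f² = 0.04 (0.3 points) and N = 200, 100 per condition. With d = 2 × √0.04 = 0.40, a two-sided two-sample t-test at 0.05 has power 0.80, which matches the plan. Limiting covariates to pre-intervention variables leaves this unchanged.

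**2. Does the text admit these variables?**
- *Timing:* the rule states none.
- *Label:* heart rate, type and context are called covariates.
- *When measured:* during the intervention.
- *Affected by assignment:* yes. Table 3 goals rise from 55% to 70% of maximum heart rate, with mean (55 + 57.5 + 60 + 62.5 + 65 + 67.5 + 70 + 70)/8 = 63.4%. No heart-rate goal is described for the affect condition.
- *Likely to meet p<.10:* plausible. Counting only 200 participants, |r| above 0.117 suffices, and the Background says type and context explain part of the variation in affective response.

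Everything in steps 3 to 6 is illustration on assumed inputs.

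**3. H1, affective response, adjusted for session heart rate.** Adjusted difference = 0.30 + b × gap. Here b is the within-condition slope of affect on heart rate, and gap is the excess heart rate under intensity goals in points of %HRmax.
- Pathway only: b = −0.01, gap 2.5 gives 0.275; b = −0.02, gap 5 gives 0.20; b = −0.02, gap 10 gives 0.10.
- Shared daily cause and no pathway: the cause moves heart rate 4 points and affect 0.3 points per SD, with residual heart-rate SD 6. Then b = (4 × 0.3)/(36 + 16) = 0.0231, and gap 5 gives 0.415 (simulated 0.416).

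**4. Physical activity, adjusted for daily mean heart rate.** Adjusted = τ(1 − r²) + r × (SD activity/SD heart rate) × g × sessions per week. Assumed SDs are 30 min/day and 3 bpm (ratio 10), and r is the within-person correlation. An excess of 10 to 20 bpm over a 36-minute session gives g = 10 × 36/1,440 = 0.25 to 20 × 36/1,440 = 0.5 bpm on a session day.
- τ = 30 min/week (the plan's figure), g = 0: 28.8, 25.2 and 19.2 for r = 0.2, 0.4 and 0.6.
- τ = 0, three sessions per week: 0.2 × 10 × 0.25 × 3 = 1.5, up to 0.4 × 10 × 0.5 × 3 = 6 min/week, in favour of affect-based goals when no effect exists.

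**5. Physical activity, complete-case with session heart rate, type or context.** The activity outcome is daily, but these covariates exist only where activity took place (for session heart rate, more than 10 minutes). Suppose 3 × 30 = 90 min/week rises by 30. As 3 × 40, 3.5 × 34.3 or 4 × 30, the model sees +10, +4.3 or 0 min per active day. This holds whether evening sessions follow the schedule under Instrumentation ("are scheduled to be sent at the same time every day") or the Intervention section ("On days participants have planned to do physical activity (according to the Sunday scheduling survey), they will engage in two goal sessions"). Affective response during activity is not affected in this way, because its prompts "are triggered when Fitbit sensors detect physical activity via moving average heart rate max" and inactive days have no such outcome to lose.

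**6. H2 power if part of the effect is adjusted away.** Enrolment of 360 less about 30% is 360 × 0.70 = 252, or 126 per level.

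| Effect lost | d | 100 per level | 126 per level |
|---|---|---|---|
| 0% | 0.400 | 80% | 88.5% |
| 9% | 0.364 | 73% | 82% |
| 32% | 0.272 | 48% | 58% |
| 40% | 0.240 | 39% | 48% |

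In simulation (24 records per person, 50% or 80% of the effect running through matched recommendations), adjusting for type or context lost under 1% with even preferences, 5% to 12% with a 3:1 skew, and 20% to 40% with a 10:1 skew.

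**The case against.** The best defence is that the authors meant baseline variables. The rule follows six person-level confounders, the baseline battery carries the covariate label, and Aim 1 commits to intent to treat. The labels under Instrumentation may be meant for Aims 2 and 3. This is a plausible reading and it stands as such, but no sentence says so, and two analysts following the text could fit different models.

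Several stronger inferences are tempting and not supported:

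- *That the plan will adjust H1 or H2 for these variables.* No section places them in those models, and entry depends on the observed association.
- *That H2 power would collapse.* The large losses need a 10:1 preference skew that nothing in the documents supports. Recommendations are each person's own top three, so raw categories track assignment poorly. With the planned enrolment, a 9% loss leaves power above 80%.
- *That a false activity gain could reach 14 min/week.* That needs a 36-minute session every day (0.4 × 10 × 0.5 × 7), or 252 min/week. Participants enter at under 60 min/week of structured activity, and the Intervention section ties goal sessions to planned days.
- *That inactive days will be lost.* This holds only for a complete-case model. The plan considers imputation and sensitivity analyses, and a no-activity category could keep those days for type and context. Continuously recorded heart rate avoids the loss, but has the problem in step 4. Conversely, if the daily evening check-in were used as the affect outcome, inactive days would be at risk there too.

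**Conclusion.** The point holds as a defect in the rule's wording. As written, the rule admits on-treatment heart rate, activity type and context into the H1 and H2 models for affective response and physical activity. If they enter, the estimate is not the intent-to-treat effect that Aim 1 says is tested. It is not evidence that a biased analysis is planned.

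The size cannot be derived from the documents. The illustrations show only that the direction is open (0.30 points becoming 0.10 to 0.42) and that a null activity effect could appear as about 1.5 to 6 min/week at three sessions per week. They rest on assumed slopes, heart-rate gaps, SDs, correlations and session frequency. The text should be corrected before the analysis, because an instruction followed literally could give a wrong answer.

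**What to change.** Add to the Comparison Study analysis section: covariates in the H1 to H3 treatment-effect models, including any chosen by the p<.10 rule, must be measured before the intervention starts, meaning in the baseline questionnaire or the run-in week. Define the start as the end of the run-in, because the Methods date study participation from the run-in's first day and Table 1 lists random assignment before it. Design terms such as period and sequence remain allowed.

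State that heart rate, activity type, context and other on-treatment measures are kept for mediation, moderation or descriptive analyses. Affective response stays as the level-1 predictor in the planned H3 interaction model. The p<.10 rule itself need not be removed for this purpose, and run-in activity as a covariate for the activity outcomes is optional.

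The cost is analysis-plan wording only. The baseline and run-in data are already collected, and the planned N and power are unchanged.

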Official Title: Using Real-Time Data Capture to Examine Affective Mechanisms as Mediators of Physical Activity Adherence in Interventions: Formative Study

NCT #: NCT06125964

Document: Study Protocol

Date: 04.02.25

Study Procedures

1. Background/Rationale

Cancer is responsible for 600,000 deaths per year in the United States. Of these cases, 15% are potentially avoidable through adequate physical activity and weight maintenance.¹ Despite public health guidelines outlining the frequency, duration, and intensity of exercise needed for these protective benefits, however, large-scale accelerometry research reveals that more than 95% of American adults remain physically inactive.² To increase the probability of physical activity engagement, researchers have previously manipulated individual cognitions,^{3,4} targeting constructs such as self-efficacy, outcome expectancies, and intentions.⁵⁻¹⁰ These interventions have had limited success. Research is desperately needed to elucidate novel mechanisms—beyond cognitive processes—that might change physical activity behaviors.

The type, context, and affective responses surrounding physical activity engagement represent valuable mechanisms that might be contributing to the exercise intention-behavior gap.¹¹ Recent evidence suggests that affect, independently of cognitive processes, is a powerful predictor of physical activity engagement and enjoyment.¹²⁻¹⁶ Exercise itself elicits robust changes to emotional states, triggering affectively-charged motivations that—per incentive salience theory—lead to pursuit or avoidance of future associated behaviors.¹⁷ While many individuals react positively to light intensity exercise and negatively to vigorous intensity exercise,¹⁸ great inter-individual variability exists in the affective response to moderate intensity physical activity.¹⁹⁻²² For example, individuals with overweight/obesity or who are typically inactive are more likely to experience unpleasant feelings when exercising.²³ This can harm their intentions to maintain healthy levels of activity over time.²⁴ Research shows that part of the heterogeneity in affective response is due to the activity type (e.g., dance, yoga, brisk walking)^{25,26} and context (e.g., being with others or outdoors).²⁷⁻³⁴ Interventions that leverage activity types and contexts to strategically increase favorable affective responses might therefore improve physical activity maintenance in groups vulnerable to avoidable cancers.

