The 19-week Comparison study (N=360) will then use a Multiphase Optimization Strategy (MOST) design to determine the effects of each intervention component.^{37,38} Specifically, we will compare affect- and intensity-based goals within-persons and affect-based goal condition enhancements between-persons (Figure 1). Participants are randomly assigned to treatment groups. The study protocol begins with a run-in period (described above), followed by either affect- or intensity-based goals for the first 8-weeks, a two week washout period, and a cross-over to receive the alternate condition for the remaining 8-weeks. During the affect-based goal condition, participants also randomly receive one of four possible combinations of TYPE/CONTEXT and SAVOR enhancements: [1] affect-based goal setting alone; [2] affect-based goals + TYPE/CONTEXT; [3] affect-based goals + SAVOR, [4] affect-based goal setting + TYPE/CONTEXT + SAVOR.

Figure 1. Comparison Study Design

Note. ^a Brief savoring experiences; ^b Tailored recommendations for activity types and contexts to satisfy important psychological needs.

Intervention

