The intensity-based goal condition asks participants to maintain a certain target heart rate range during physical activity (for example, “Today, your goal is to maintain a minimum heart rate of 130 bpm during physical activity.”). Starting heart rate reflects the approximate age-adjusted heart rate max, with goals progressively increasing from 55% to 70% heart rate max across 8 weeks (i.e., the moderate intensity activity range) for the Comparison Study (see Table 3), and from 55% to 60% across 2 weeks for the Formative Study. Research staff will show participants how to monitor their heart rate using their Fitbit smartwatch. Specifically, when they press the physical activity button on the Fitbit smartwatch (described above), the watchface will display real-time heart rate in addition to activity duration.

Table 3. Comparison Study Minimum Heart Rate Goals

Week	% HRmax
1	55.0%
2	57.5%
3	60.0%
4	62.5%
5	65.0%
6	67.5%
7	70.0%
8	70.0%

The affect-based goal condition asks participants to engage in either (1) a type (50% of daily goals) or (2) a context (50% of daily goals) of physical activity that allows them to experience positive affect. Goals focused on context are randomly generated to suggest that the participant performs activity (1) in a place; (2) in a social situation; or (3) while listening to something that makes them feel good.

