AIM 1: Determine whether affective mechanisms can be experimentally manipulated. In the Formative study, descriptive statistics (means, frequencies) will assess acceptability and feasibility of content, delivery methods, device usage, engagement, and raw values for change in affective mechanisms. The Comparison study will use an “intent to treat” approach to test the (1) within-subject effects of affect- vs. intensity-based goals (H1), (2) between-subject effects of affect-based goals with vs. without TYPE/CONTEXT (H2), and (3) between-subject effects of affect-based goals with vs. without SAVOR (H3) on the primary outcome (affective responses and affectively-charged motivations) and secondary outcome (physical activity). We will use random-effect regression models (level 1-days, level 2-subjects), which adjust for clustering within subjects and incorporate random effects.¹⁰⁷ Each treatment effect and each outcome will be tested in separate models. We will examine cross-level interactions between affect-based goals with vs. without savoring (level 2) and affective responses (level 1) to test H3.

AIM 2: Determine whether affective mechanisms mediate effects of interventions on physical activity (Comparison Study). Multilevel mediation will be tested using a 1-1-1 strategy that fits a set of simultaneous equations using path analysis in R.¹⁰⁸ Analyses will test the effects of intervention engagement on same-day/same-week affectively-charged motivations and affective response; the effects of affectively-charged motivations on same-day/same-week physical activity and the effects of affective responses on next-day/next-week physical activity; the indirect effects of intervention engagement on same- and next-day/same- and next-week physical activity via affective mechanisms (H4); and the total effects (mediated plus unmediated) of intervention engagement on physical activity.

AIM 3: Explore cross-person and cross-situation moderating effects (Comparison study). We will add interaction terms for time-varying and time-invariant effect moderators (H5).¹⁰⁹

Dissemination of Findings

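### H1 rests on about 200 within-person period differences, but the plan argues its precision from 22,400 days and does not say which random effects the H1 model contains

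*Combined protocol and SAP*

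**What the plan says.** **Design.** Section 5 (Methods, Intervention Period) describes a run-in, 8 weeks of one goal condition, then "a two week washout period, and a cross-over to receive the alternate condition for the remaining 8-weeks". Order is randomised. The goal condition therefore changes once per person.

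**Model.** Under AIM 1 in the Data Analysis section (Comparison Study), H1 is the within-subject comparison of affect-based with intensity-based goals, on affective outcomes (primary) and physical activity (secondary). The model statement is: "We will use random-effect regression models (level 1-days, level 2-subjects), which adjust for clustering within subjects and incorporate random effects". No condition slope, period effect or residual correlation is named.

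**Power.** The same section says "Power estimates were evaluated using Monte Carlo simulations in Mplus", but gives no inputs or results for H1. The planned effect on affective response is f² = 0.04, "representing a 0.3 point increase on a 5-point affect scale". N=200 after attrition is justified for the between-subject hypotheses H2 and H3. For H1 the text says only "To detect within-subject effects (H1 and H4), our level-1 sample sizes will be much larger", gives 200 × 4 × 4 × 7 as an example, and concludes: "Thus, we should have sufficient power to detect very small effects for the remaining associations".

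**The concern.** Days within one 8-week period all share the same condition. Extra days sharpen each person's period mean, but they say nothing more about how the condition effect differs from person to person. A model with a subject intercept alone treats that variation, and any carry-over of one day's value into the next, as independent daily noise that averages out. The standard error for H1 is then too small.

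The plan gives some reason to expect such variation. The Background says "great inter-individual variability exists in the affective response to moderate intensity physical activity", and the Intervention section has the heart-rate goals rising "across 8 weeks (i.e., the moderate intensity activity range) for the Comparison Study". H5 predicts larger effects in people with lower self-regulatory capacity.

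H1 is the head-to-head comparison of the two goal types. With too small a standard error it could be declared positive when the average effect is zero, and its 95% interval would be too narrow whatever the true effect. Recruiting more people would not cure this, because the true and the reported standard errors shrink together.

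**Working it through.** **1. The plan's own figures.** A one-degree-of-freedom F test with f² = 0.04, N = 200 and two-sided α = 0.05 (sidedness assumed) has power 0.804, so N=200 reproduces for H2 and H3. For H1, 200 × 4 × 4 × 7 = 22,400 days = 200 people × 2 periods × 56 days. That is 200 × 2 = 400 person-periods, or 200 paired differences.

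**2. Inputs not in the documents (assumptions).**
- s, the between-person SD of the affect-minus-intensity effect in day-level SD units: 0.1, 0.2 and 0.5. The share of within-person variance lying between periods is (s²/2)/(1 + s²/2) = 0.5%, 2.0% and 11.1%.
- n, observed days per period: 56 (every day) or 24 (for example 3 days a week for 8 weeks). The EMA section records affective response only when activity is detected, so 24 is the closer case for that outcome.
- Lag-1 autocorrelation of daily values: 0 or 0.3.

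**3. Formulas.** Let v be the variance of a mean of n days: 1/n without autocorrelation, otherwise (1/n)[1 + 2Σ(1 − k/n)ρᵏ] over k = 1 to n − 1.
- True variance of the H1 estimate = (s² + 2v)/N.
- Variance reported by an intercept-only model = 2·MSE/(nN), with MSE = [2n(1 − v) + n(s² + 2v)/2]/(2n − 1).
- False-positive rate = 2Φ(−1.96/R), where R is the ratio of true to reported standard error. Coverage of the 95% interval is 1 minus this rate.
- Detectable effect (80% power) = 2.80 × true standard error.

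**4. One case in full (n = 56, s = 0.2, no autocorrelation).** True variance = (0.04 + 2/56)/200 = 0.000379, SE 0.0195. MSE = (110 + 2.12)/111 = 1.010, so the reported variance is 2 × 1.010/(56 × 200) = 0.000180, SE 0.0134. R = 1.449, and the false-positive rate is 2Φ(−1.353) = 0.176.

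**5. Range, no autocorrelation, N = 200.**

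| n | s | R | False-positive rate | Coverage | Detectable effect with slope |
|---|---|---|---|---|---|
| 24 | 0.1 | 1.057 | 0.064 | 0.94 | 0.060 |
| 24 | 0.2 | 1.210 | 0.105 | 0.89 | 0.070 |
| 24 | 0.5 | 1.939 | 0.312 | 0.69 | 0.114 |
| 56 | 0.1 | 1.130 | 0.083 | 0.92 | 0.042 |
| 56 | 0.2 | 1.449 | 0.176 | 0.82 | 0.054 |
| 56 | 0.5 | 2.743 | 0.475 | 0.53 | 0.106 |

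With lag-1 autocorrelation 0.3 and n = 56, v = 0.0328. The rate is 0.149 at s = 0, 0.254 at s = 0.2 and 0.498 at s = 0.5. The largest detectable effect examined (n = 24, s = 0.5, lag-1 0.3) is 0.125.

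**6. Simulation.** Two-sequence crossovers adjusted for period (N = 200, 3,000 runs per case) gave intercept-only rates of 0.179 and 0.470 (n = 56) and 0.101 and 0.301 (n = 24) at s = 0.2 and 0.5. A person-level test, which is what the condition slope amounts to in balanced data, held at 0.045 to 0.054 in all 12 cases. Mixed models were also fitted with 5% of within-person variance between periods and n = 56, where the closed form gives 0.31. The intercept-only model rejected a true null in 42 of 139 data sets and the slope model in 5 of 139; a further batch of 40 gave 17 and 4.

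**7. Power.** f² = 0.04 corresponds to d = 2√0.04 = 0.40, read here in day-level SD units (an assumption; 0.3/0.40 implies an SD of 0.75 points). In the least favourable case the true standard error is 0.125/2.80 = 0.045, so 0.40 is about 9 standard errors and power exceeds 0.99.

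**The case against.** The strongest reply is that the plan commits no error. It refers to random effects in the plural, in addition to the adjustment for clustering, and nowhere restricts them to an intercept. With two periods and one condition in each, a by-subject condition slope absorbs the person-by-period variance inside a days-and-subjects model, so no third level is needed. The count of 22,400 is correct and is described as a level-1 count, not as an effective sample size. The simulations may well have included a slope; their inputs are simply not reported. All of this stands.

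Two further points stand in part. The Background sentence concerns variability in response to moderate activity, not in the affect-minus-intensity difference, and stable differences in level go into the intercept. H5 bears on the difference directly, but it is labelled exploratory and has its own interaction terms. Heterogeneity is therefore plausible, not established. The highest rates also need s = 0.5, larger than the planned mean effect of 0.40, together with 56 observed days. For the event-contingent affect outcome, the 24-day figures are the better guide.

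Finally, the near-5% rates come mainly from a person-level test in balanced data. The mixed-model fits were few, and activity-dependent, unequal day counts were not simulated.

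What remains is that two analysts could both follow the model statement and obtain materially different H1 standard errors. The only quantity that the plan offers for H1 describes its precision only in the simpler case: no variation in the effect and no autocorrelation.

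**Conclusion.** The point holds as an underspecified analysis with a conditional consequence. H1 precision is governed by about 200 paired differences, and the plan neither says so nor names the term that respects it. If the fitted model has only a subject intercept, the nominal 5% rate becomes about 0.06 to 0.31 with 24 observed days per period and 0.08 to 0.47 with 56, for s between 0.1 and 0.5 without autocorrelation. Lag-1 autocorrelation of 0.3 alone gives about 0.15. The direction is firm. The size rests on variance values that the documents do not supply, and the mild end is close to nominal.

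A reader might infer three stronger things that the documents do not support:
- that the plan has adopted an intercept-only model or left out a required level: its wording permits the slope within the two levels named;
- that the day count is an arithmetic mistake: it is not;
- that H1 is underpowered: with the slope, the detectable effect at N=200 is about 0.04 to 0.13 SD, so the plan's conclusion about small effects broadly survives.

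**What to change.** In the AIM 1 analysis text, state that each H1 outcome is modelled by day with fixed effects for condition and period, and a random intercept and random condition slope for each participant. Autocorrelated residuals within period are optional. If that model does not converge, test H1 on each participant's two period means, adjusted for period. Settle this before the data are analysed, so that the choice cannot depend on the result.

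In the power text, keep the day count for H4. For H1, give the detectable effect from the number of people expected to have both periods, a stated range for the condition-slope SD, and the observed days expected for each outcome.

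The cost is a few sentences and one rerun of the simulation, with no change to enrolment, design or data collection. The drawback is wider H1 intervals: about 1.06 to 2.7 times those of an intercept-only model under the assumed values without autocorrelation. Power for the planned effect stays above 0.99 on the reading of d used above.
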